8.3 MULTIPLE COMPARISONS AND MULTIPLICITY

No multiple comparison adjustments are planned for analysis of this study.

8.4 ASSESSMENT WINDOWS

For efficacy and safety assessments, Baseline is defined as the measurements prior to the first dose of UT-15C in the TDE-PH-311 study.

Summary analyses will be based on the scheduled (nominal) visits with no visit windows applied.

9 STUDY POPULATION

9.1 SUBJECT ACCOUNTABILITY

A listing of subject disposition and UT-15C exposure will include subject number, treatment group in the parent study, first and last UT-15C dose date/time in the TDE-PH-311 study, date completed/discontinued the study, cut off date, study drug exposure (weeks), reason for discontinuation, and any other details regarding reason for discontinuation. The summary of subject accountability will include the number (percent) of subjects by treatment group who completed the study without early termination, the number of subjects who completed UT-15C treatment by each visit achieved, number of subjects who discontinued UT-15C treatment, and the reason for discontinuation. This summary will be provided by treatment group in the parent study and overall.

UT-15C exposure and the total subject-years of UT-15C exposure will be summarized by the treatment group in the parent study and overall.

In addition, for subjects who were in UT-15C group in the parent study (TDE-PH-310), their exposure to UT-15C in the parent study will be combined into the TDE-PH-311 study. The

overall exposure to UT-15C across both the parent study and the TDE-PH-311 study will be summarized.

9.2 ELIGIBILITY CRITERIA

The listing of entry criteria for all subjects will include whether the subject rolled over from the previous study, each subject's treatment group in the parent study, status regarding meeting all eligibility criteria (yes/no), and will include an explanation if not all eligibility criteria are met. The summary of entry criteria will include the number and percent of subjects who did meet and the number and percent of subjects who did not meet all eligibility criteria by treatment group in the parent study and overall.

In addition, a listing will be provided for protocol deviations. The listing will include the subject number, deviation date, deviation type, deviation severity, and deviation description by treatment group in the parent study.

9.3 OTHER DESCRIPTIONS OF STUDY POPULATION

9.3.1 Demographics

The listing of subject demographics will be organized by treatment group in the parent study, and will include subject number, country, assessment date, date of birth, subject age (years), sex, ethnicity, race, height, weight, and body mass index (BMI). The age will be calculated based on the first UT-15C dose date in the TDE-PH-311 study. The summary of demographics will include descriptive statistics for age (years) at first dose of UT-15C and categorical summaries for age (<65 and ≥65 years), sex, ethnicity, race, height, weight, and BMI, where weight is the measure before the first dose of UT-15C for the TDE-PH-311 study and height is obtained from the parent study.

9.3.2 Baseline Characteristics

Baseline characteristics include 6MWD, 6MWD category (≤380 m versus >380 m), Borg dyspnea score, and WHO Functional Class, and will be summarized by treatment group in the parent study and overall. Baseline measures are defined as the last measurement prior to the first UT-15C dose in the TDE-PH-311 study.

9.3.3 PAH History

The listing of PAH history will be organized by treatment group in the parent study, and will include the subject number, the date of initial PAH diagnosis, number of years since PAH diagnosis, etiology, WHO Functional Class at Baseline, 6MWD at Baseline, Borg dyspnea score at Baseline, background PAH therapy (endothelin receptor antagonist [ERA] alone, phosphodiesterase type 5 inhibitor [PDE-5I] alone, or soluble guanylate cyclase [sGC] stimulator alone), and background PAH medication name. The number of years since PAH diagnosis will be calculated based on the first UT-15C dose date in the TDE-PH-311 study. The summary of PAH history will include descriptive statistics for years since PAH diagnosis and categorical summaries for etiology and background PAH therapy at randomization in the parent study.

9.3.4 Concomitant Medications

The listing of concomitant medications will be organized by treatment group in the parent study, and will include subject number, whether the subject has had any concomitant medications, and all concomitant medications (including PAH medications) that were reported on or after the date of the first UT-15C dosing in the TDE-PH-311 study. The concomitant medications will be listed by verbatim term, WHO Drug Dictionary (WHO-DD) standard name, start and stop dates, condition treated/indication, whether the concomitant medication is ongoing from parent study, and whether or not the concomitant medication is ongoing at the end of the study. Summaries will be provided for medications ongoing from the parent study and for those added in the TDE-PH-311 study. Each summary will be provided by treatment group in the parent study and overall, and will include the number (percent) of subjects reporting each medication (based on the WHO-DD medication name) and the number of records for each medication.

9.3.5 UT-15C Dosing

In the TDE-PH-311 study, UT-15C dosing information will be collected on a monthly basis. A listing and a summary will be provided for UT-15C dosing. The listing will be organized by treatment group in the parent study, and will include the subject number, dose recording date, and the actual dose (in milligrams) for morning, mid-day, and evening.

The UT-15C dose will be summarized by analysis visit. The summary will also include the number and percent of subjects in each dose category by treatment group in parent study and overall. The same summary table will be repeated by each background PAH therapy. The dose categories include UT-15C drug dose (3 times daily [TID]) <1 mg, 1 to <2 mg, 2 to <4 mg, 4 to <6 mg, 6 to <8 mg, 8 to <10 mg, 10 to <12 mg, and ≥ 12 mg.

10 EFFICACY ANALYSES

10.1 6-MINUTE WALK TEST

The listing of the 6MWT will be organized by treatment group in the parent study, and will include subject number, analysis visit, assessment date/time (day), last UT-15C dose date/time (day), the last UT-15C dose (in milligrams), hours from last UT-15C dose to 6MWT, 6MWD results, Borg dyspnea scores, use of supplemental oxygen, and any circumstances affecting the 6MWT. The summaries of 6MWD will be provided by treatment assignment in the parent study (UT-15C or placebo) by visit, PAH etiology (idiopathic, heritable, associated with connective tissue disease, and other), Baseline WHO Functional Class, and quartiles of the last UT-15C dose. The summaries will include descriptive statistics for 6MWD measure at each analysis visit and the change from Baseline. Baseline is defined as the last 6MWD measured prior to the first dose of UT-15C in the TDE-PH-311 study.

Achievement of a walk distance of at least 440 m by each analysis visit will be summarized by treatment group in the parent study and overall. Achievers and non-achievers will then be summarized based on their Baseline walk (≤ 440 m vs >440 m) by treatment group in the parent study and overall.

10.2 BORG DYSPNEA SCORE

Borg dyspnea score information will be listed as part of the 6MWD. The summary of the Borg dyspnea score will be provided by treatment group in the parent study. The summaries will include descriptive statistics for measurements at each analysis visit and the change from Baseline values. Baseline is defined as the last Borg dyspnea score measured prior to the first dose of UT-15C in the TDE-PH-311 study.

10.3 WHO FUNCTIONAL CLASS

WHO Functional Class information will be listed by treatment group in the parent study, and will include subject number, analysis visit, assessment date (day), and WHO Functional Class. The summaries of the WHO Functional Class will be provided by treatment group in the parent study. The summaries will include descriptive statistics for measurements at each analysis visit and the change from Baseline values. Baseline is defined as the last WHO Functional Class assessed prior to the first dose of UT-15C in the TDE-PH-311 study.

11 SAFETY ANALYSES

11.1 ADVERSE EVENTS

AEs are captured from the time the Informed Consent Form is signed. Any AEs that are ongoing at the Study Termination Visit from study TDE-PH-310 are recorded as continuing AEs in TDE-PH-311 study. All AEs with an onset date on or after the first dose of UT-15C in the TDE-PH-311 study or AEs ongoing from the parent study will be included in data listing and summaries.

The AEs will be coded using the Medical Dictionary for Regulatory Activities (MedDRA), and all summaries will utilize the Preferred Term (PT) and/or System Organ Class (SOC). All AEs and serious AEs will be organized by treatment group in the parent study, and listed by subject, including onset date (day), cessation date (day), verbatim term, corresponding PT and SOC, seriousness, date AE became serious, severity, frequency, relationship to study drug, action taken with study drug, and outcome.

The overall summary of AEs includes the number of subjects with any AE, the number of subjects with any study drug-related AEs, the number of subjects with AEs leading to study drug withdrawal, the number of subjects with any serious AEs, the number of subjects with any severe AEs, and the number of subjects with any study drug-related severe AEs.

The summaries of AEs by SOC and PT will be provided by treatment group in the parent study and overall. The summaries of AEs, serious AEs, severe AEs, AEs probably or possibly related to UT-15C, serious AEs probably or possibly related to UT-15C, and AEs

leading to permanent discontinuation of UT-15C will include the number of subjects (percent of subjects) and number of events for each reported PT.

The summary of AEs adjusted for UT-15C exposure will include the number of subjects (percent of subjects) and number of events for each reported PT, as well as the number of events per patient-year of exposure.

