TDE-PH-304 is a long-term, open-label, international, Phase 3 studies designed to provide access to UT-15C for subjects previously enrolled in studies TDE-PH-301, TDE-PH-302, TDE-PH-308, or other specified studies conducted during the UT-15C development program. Secondary objectives of the study are to assess the long-term safety of UT-15C in PAH patients and to assess the effect of continued therapy on exercise capacity via 6MWD following one year of treatment with UT-15C. As of 01 September 2015, over 896 subjects were enrolled, representing 2377.7 patient-years of exposure. The mean and maximum duration of exposure was 138.8 and 444.9 weeks (2.66 and 8.53 years), respectively. The mean dose of oral treprostinil achieved was 3.9, 4.5, 4.8, 5.0, 5.5, 5.9, and 5.9 mg BID at 1 year (N=605), 2 years (N=472), 3 years (N=337), 4 years (N=230), 5 years (N=119), 6 years (N=77), and 7 years (N=37), respectively. Adverse Events were typical of prostacyclin

therapy; laboratory findings were unremarkable and did not suggest any specific safety concerns related to long-term treatment with UT-15C. Following 12 months of oral treprostinil treatment, the mean 6MWD increased by +25 meters as compared with Baseline. Kaplan-Meier analysis of subject survival demonstrated 1-, 2-, and 3-year survival estimates of approximately 93.6%, 87.9%, and 82.2%, respectively.

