7 EXPERIMENTAL PROCEDURES

7.1 TREATMENT PHASE

7.1.1 *Baseline/Study Entry*

All data collected at the subject's Study Termination Visit during TDE-PH-310 and prior to initiating open-label study drug will serve as Baseline/Study Entry assessments for this study. Following completion of the Study Termination assessments for a subject and entry of required data into the interactive voice or web response system (IVRS/IWRS), the site

personnel will be unblinded to that subject's treatment assignment. Subjects must sign an ICF and meet inclusion/exclusion criteria specific to this protocol. The recommended sequence of events for Baseline/Study Entry is displayed below:

- Informed consent (prior to any study assessments)
 - Inclusion/exclusion criteria
 - Vital signs (following at least 5 minutes of rest)*
 - Physical examination*
 - WHO Functional Class*
 - AE assessment*
 - 6MWT/Borg dyspnea score (for subjects randomized to UT-15C in TDE-PH-310, the 6MWT to be initiated 3 to 6 hours after the last dose of UT-15C; 6MWT to be conducted following at least 5 minutes of rest; Borg dyspnea score to be conducted immediately following 6MWT)*
 - Urine pregnancy test (for WOCBP)*
 - Clinical laboratory assessments*
 - Plasma NT-proBNP*
 - Study drug dosing (for subjects randomized to placebo in TDE-PH-310, the initial dose of UT-15C in TDE-PH-311 should be taken at the study site)
 - Drug accountability
 - Concomitant medications*
 - Weekly telephone calls are highly recommended especially after any dose changes
- *assessments conducted during the Study Termination Visit for the TDE-PH-310 study will not need to be repeated*

The AEs that were ongoing at the end of the TDE-PH-310 study will be recorded as ongoing events for this open-label study. Concomitant medications that were ongoing at the TDE-PH-310 Study Termination Visit will be recorded in the eCRF for the open-label study. Once the subject signs the ICF for this study, all ongoing AEs must be recorded and documented on the eCRF. All AEs and concomitant medications will be reported continuously for the duration of the study. Phone calls to the subject must begin within 1 week of the subject receiving the first dose of study drug and continue to be made weekly for the first 12 weeks of the study. After the first 12 weeks, phone calls must be made at least monthly. Dose titration should occur as needed in accordance with Section 6.1.

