12 APPENDICES**12.1 LIST OF TABLES**

Table titles suggested here may be altered or edited as appropriate by the clinical data programmers while maintaining the original intent of the summary.

Table Number	Table Title
14.1.1	Summary of Subject Accountability
14.1.2	Summary of UT-15C Exposure
14.1.3	Summary of UTC Exposure in TDE-PH-310 and TDE-PH-311 Studies
14.1.4	Summary of Demographics
14.1.5	Summary of Baseline Characteristics
14.1.6	Summary of PAH History
14.1.7	Summary of Study Entry Criteria
14.1.7.1	Summary of UT-15C Dosing
14.1.7.2	Summary of UT-15C Dosing by Background PAH Therapy
14.1.8.1	Summary of Concomitant Medications Ongoing from the Previous Study
14.1.8.2	Summary of Concomitant Medications Added in TDE-PH-311 Study
14.2.1.1	Summary of 6MWD (meter) by Visit
14.2.1.2	Summary of Borg Dyspnea Score by Visit
14.2.1.3	Summary of 6MWD (meter) by PAH Etiology
14.2.1.4	Summary of 6MWD (meter) by Baseline WHO Functional Class
14.2.1.5	Summary of 6MWD (meter) by Quartiles of the Last UT-15C Dose
14.2.1.6	Summary of 6MWD Achieving > 440 Meters by Visit
14.2.1.7	Summary of 6MWD Achieving >440 Meters by Baseline 6MWD Category
14.2.1.8	Summary of WHO Functional Class by Visit
14.3.1.1	Overall Summary of Adverse Events
14.3.1.2	Summary of Adverse Events by System Organ Class and Preferred Term
14.3.1.3	Summary of Serious Adverse Events by Preferred Term
14.3.1.4	Summary of Severe Adverse Events by Preferred Term
14.3.1.5	Summary of Serious Adverse Events Probably or Possibly Related to UT-15C by Preferred Term
14.3.1.6	Summary of Adverse Events Probably or Possibly Related to UT-15C by Preferred Term
14.3.1.7	Summary of Adverse Events Leading to Permanent Discontinuation of UT-15C
14.3.1.8	Summary of Disease-Related Events
14.3.1.9	Summary of Adverse Events Adjusted for Length of UT-15C Exposure
14.3.2.1	Listing of Deaths
14.3.2.2	Summary of Deaths
14.3.2.3	Listing of Serious Adverse Events

Table Number	Table Title
14.3.4.1	Summary of Hematology Data
14.3.4.2	Summary of Hematology Shifts from Baseline
14.3.4.3	Summary of Clinical Chemistry Data
14.3.4.4	Summary of Clinical Chemistry Shifts from Baseline
14.3.4.5	Summary of Urinalysis Data
14.3.4.6	Summary of Vital Signs

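### Table 14.3.1.9 counts AEs that began before the first TDE-PH-311 dose, so the numerator of its per-patient-year rate does not match its exposure denominator, which is not named

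*SAP*

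**What the plan says.** SAP 11.1 states which AEs enter the listing and summaries: those with onset on or after the first TDE-PH-311 dose, "or AEs ongoing from the parent study will be included in data listing and summaries". The same section plans an exposure-adjusted summary giving subjects (%), event counts, "as well as the number of events per patient-year of exposure", for each preferred term. SAP 12.1 lists it as Table 14.3.1.9, "Summary of Adverse Events Adjusted for Length of UT-15C Exposure". It has no inclusion rule of its own.

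Carry-over is mandatory. Protocol 7.1.1 says: "The AEs that were ongoing at the end of the TDE-PH-310 study will be recorded as ongoing events for this open-label study". Protocol 3.3.2.4 and 9.2 repeat the instruction.

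SAP 9.1 describes two exposure summaries. The first is "UT-15C exposure and the total subject-years of UT-15C exposure will be summarized by the treatment group in the parent study and overall". The second, introduced as an addition, concerns former UT-15C subjects: "their exposure to UT-15C in the parent study will be combined into the TDE-PH-311 study". SAP 11.1 does not say which one supplies the patient-years.

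For concomitant medications, SAP 9.3.4 already makes the split that is missing for AEs: "Summaries will be provided for medications ongoing from the parent study and for those added in the TDE-PH-311 study".

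**The concern.** An event rate divides events that begin during time at risk by that time. An AE carried over from TDE-PH-310 began before the TDE-PH-311 clock started. In a former placebo subject it began before any study UT-15C, yet it would be counted in a table described as adjusted for UT-15C exposure.

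Long-term safety is the first secondary objective (Protocol 2.2). Table 14.3.1.9 is the only AE table in SAP 12.1 that adjusts for exposure, and follow-up is open-ended with no concurrent control. The distortion is largest for preferred terms that are often ongoing at rollover. It can also differ between the two parent-study groups, so the columns could differ even when AEs begin on study at the same rate. A reader could not correct this from the table itself.

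**Working it through.** The plan states no AE rate, so there is no figure to reproduce. The direction follows from the definitions; the sizes below are illustrations.

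**Inputs**
- L: true rate of AEs with on-study onset, per patient-year. Not in the documents; assumed 3, range 1 to 5.
- c: carried-over AEs per subject. Not in the documents; assumed 1, range 0.5 to 2.
- T: mean TDE-PH-311 exposure in years. Not in the documents. Reference points are 1 year (assumed), 2.66 years and 6 years. The second is from the earlier extension study TDE-PH-304 (Protocol 1.2.4): "The mean and maximum duration of exposure was 138.8 and 444.9 weeks", the mean being 2.66 years. The third is the approximate study length in Protocol 3.6, used as an upper bound.
- P: mean parent-study UT-15C exposure in years. Zero for former placebo subjects; assumed 1 for former UT-15C subjects.

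**Step 1. TDE-PH-311 exposure as denominator**

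Planned rate = (L×T + c)/T = L + c/T.

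Relative excess = c/(L×T), that is, carried-over events divided by on-study-onset events. This ratio needs no assumption and applies to each preferred term and each group.

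With c = 1:

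| T (years) | Excess c/T per patient-year | L = 1 | L = 3 | L = 5 |
|---|---|---|---|---|
| 1 | 1.00 | 100% | 33.3% | 20.0% |
| 2.66 | 0.38 | 37.6% | 12.5% | 7.5% |
| 6 | 0.17 | 16.7% | 5.6% | 3.3% |

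The excess is proportional to c. At T = 2.66 and L = 3, L×T = 7.98, so c = 0.5 gives 0.5/7.98 = 6.3% and c = 2 gives 2/7.98 = 25.1%.

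**Step 2. Combined TDE-PH-310 and TDE-PH-311 exposure as denominator**

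Planned rate = (L×T + c)/(P + T).

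- Former placebo subjects: P = 0, so the result is that of Step 1 and the rate is still too high by c/T.
- Former UT-15C subjects: parent-study time is added, but parent-study AEs that resolved before rollover are not. If L is the same in both studies, the rate falls below L whenever c < L×P. With c = 1, L = 3, T = 2.66 and P = 1: (7.98 + 1)/3.66 = 8.98/3.66 = 2.45 against a true 3, about 18% too low.

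Neither denominator gives a matched rate in both groups.

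**Step 3. Effect on the two parent-study columns**

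Take one preferred term with an on-study onset rate of 0.30 per patient-year in both groups, T = 2.66, and c = 0.4 (former UT-15C) and 0.1 (former placebo), all assumed except that T is borrowed from TDE-PH-304.

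- Former UT-15C: 0.30 + 0.4/2.66 = 0.45.
- Former placebo: 0.30 + 0.1/2.66 = 0.34.
- Ratio: 1.33, where the true ratio is 1.

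**The case against.** **The denominator is not stated.** A reader might infer that every rate in the table is too high. That holds only on TDE-PH-311 exposure. This is the natural reading, because SAP 9.1 offers combined exposure only as an addition and the title of Table 14.3.1.9 resembles that of the single-study exposure table (14.1.2) rather than the two-study one (14.1.3). But SAP 11.1 does not say so, and Step 2 shows that the direction can reverse for former UT-15C subjects. Only the former placebo result is independent of this choice.

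**The SAP does not say the table estimates new-onset incidence.** It openly includes ongoing AEs, and an effect that persists on drug is relevant to long-term safety. This supports displaying such AEs, not adding them to a rate. Dividing an event that began earlier by later person-time gives neither an incidence nor a prevalence. The argument for inclusion is weakest for former placebo subjects.

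**The AE listing shows onset dates.** Carried-over events can therefore be identified. That makes the fix cheap, but a reader should not have to rebuild a rate table from a listing.

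**Data cuts.** A reader might also infer that carry-over is what would make rates from successive cuts (SAP 5) non-comparable, or that removing it would make them comparable. The documents support neither. Former placebo subjects start UT-15C and titrate in this study (Protocol 6.1), so the onset rate may itself change over time, and rates from cuts with different mean exposure could differ even when correctly counted.

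**The size is entirely assumed.** This stands. No passage gives c or L, and T = 2.66 comes from a different extension study with twice-daily dosing.

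**Conclusion.** The point holds as a mismatch between numerator and denominator. Followed as written, SAP 11.1 puts AEs that began before the first TDE-PH-311 dose into a rate per patient-year whose denominator is unnamed. On TDE-PH-311 exposure every rate with at least one carried-over event is too high, as a measure of on-study onset, by c/T. For former placebo subjects this is so on either exposure; for former UT-15C subjects on combined exposure, the rate could be too low.

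The actual size cannot be computed from the documents. For c = 1, the illustrations run from 3.3% to 100%, depending on the assumed L and T. The 1.33 group ratio shows what is possible and is not a prediction.

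The table is descriptive and no hypothesis is tested (Protocol 10.3), so the consequence is limited to how the long-term safety rates are read. It should be fixed because the rule as stated gives a wrong rate and correcting it is cheap.

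**What to change.** Amend SAP 11.1 as follows.

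1. In Table 14.3.1.9, base the event count, the rate and the subjects (%) column on AEs with onset on or after the first TDE-PH-311 dose. A worsening recorded as a new AE counts by its own onset date. Add a footnote that these counts differ from those in Table 14.3.1.2.
2. State that the denominator is TDE-PH-311 UT-15C subject-years.
3. Show AEs ongoing from the parent study separately, by parent-study group, following the concomitant-medication model in SAP 9.3.4. Flag those that became serious or led to permanent discontinuation during TDE-PH-311.

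The other AE tables may keep the present inclusion rule.

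The cost is SAP wording, one added display and some programming. Onset date, date the AE became serious and action taken are already in the planned AE listing, so no new data, visits or protocol amendment are needed.

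There are two downsides. Reported rates will fall somewhat and will no longer include AEs that persist on drug from the parent study, so the display in item 3 must accompany the table. A carried-over AE that worsens but is not recorded as a new AE will also leave the rate. Protocol 15.4 asks only for maximum intensity, so no rule based on change in severity is proposed; such an event remains visible in item 3.

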Secondary Objective(s)	
 To assess the long-term safety of oral UT-15C To assess the effect of continued long-term therapy with UT-15C on exercise capacity (6-Minute Walk Distance [6MWD]/Borg dyspnea score), World Health Organization (WHO) Functional Class, and N-terminal pro-brain natriuretic peptide (NT-proBNP) (at Week 48 only)
Exploratory Objective	
 Optional evaluation of pharmacogenomics
Study Design	Multi-center, open-label study for eligible patients who participated in TDE-PH-310
Sample Size	Up to 850 subjects from Protocol TDE-PH-310 will be enrolled.
Summary of Subject Eligibility Criteria	Participation and completion of required visits from TDE-PH-310. Discontinued due to clinical worsening in TDE-PH-310. All ongoing subjects at the time the number of adjudicated clinical worsening (morbidity or mortality) events specified in Protocol TDE-PH-310 has occurred will be eligible to participate in this open-label study.
Drug Dosage and Formulation	
All subjects will receive oral treprostinil diethanolamine (UT-15C) sustained release tablets. Study drug will be provided in 0.125, 0.25, 0.5, 1.0, and 2.5 mg sustained-release (SR) tablets to be administered 3 times daily (TID) immediately after (~10 minutes) consuming food.
 
For subjects who were randomly allocated to UT-15C in TDE-PH-310, the initial dose of UT-15C in the open-label study will be based upon their final dose in TDE-PH-310. Dose escalation of UT-15C may occur in either 0.125 or 0.25 mg increments no more than every 24 hours based on adverse effects and signs and symptoms of PAH.
 
For subjects who were randomly allocated to placebo in Protocol TDE-PH-310, dosing of UT-15C will be initiated at 0.125 mg TID. Dose escalations can occur no more than every 24 hours (3 consecutive doses) in 0.125 mg increments TID during the first 4 weeks of the study. Following 4 weeks

	of treatment, dose escalation may occur no more than every 24 hours in either 0.125 mg or 0.25 mg increments TID every 24 hours. There is no maximum dose specified for this study. Note that sudden dose escalations or reductions may lead to intolerable adverse effects or worsening PAH and gradual dose titrations are recommended to reduce the risk to subjects.
Control Group	None
Route of Administration	Oral

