10.3 ANALYSIS PLAN

All safety and efficacy data will be summarized in tables and listings and analyzed for trends over time. No formal hypothesis testing is planned.

The safety population will be defined as all subjects in the study that received UT-15C at any time during the course of the study. Safety analyses will be performed on the safety population. All AEs as recorded by the Investigators will be assigned MedDRA preferred terms by the Sponsor for reporting purposes.

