5 SEQUENCE OF PLANNED ANALYSES

Along with the safety information from the parent study (TDE-PH-310), safety information from the TDE-PH-311 study will be provided to the Data Monitoring Committee (DMC) periodically for safety review.

At the time of study completion and unblinding for the parent study (TDE-PH-310), a data cut for the TDE-PH-311 study will be performed to facilitate the analysis for the TDE-PH-311 study. Analyses based on additional data cuts and the final analyses at the time of study closing will be performed separately.

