6 SAMPLE SIZE CONSIDERATIONS

No formal sample size calculation has been conducted. All eligible subjects from the parent study (TDE-PH-310) may be enrolled into this open-label extension study.

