11.2 DISEASE-RELATED EVENTS

Disease-related events will be listed by the subject number, treatment group in parent study, and events (yes/no). The summary will include the number (percent) of subjects who reported each symptom by treatment group in the parent study and overall. Disease-related events include abdominal pain, anorexia, ascites, chest pain, cool extremities, cor pulmonale, cough, cyanosis, dizziness, dyspnea, general edema, hemoptysis, fatigue, hypoxia, loss of consciousness, nausea, orthopnea, pallor, palpitations/cardiac arrhythmia, paroxysmal nocturnal dyspnea, pulmonary hypertension exacerbation, syncope, tachycardia, weight loss/gain, vasovagal reaction, and vomiting.

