11.3 DEATHS

All deaths will be listed (including those occurring within 30 days of the last UT-15C dose) by subject, and will include the subject number, treatment group in the parent study, date of assessment (day), whether subject died, date of death (day), and cause of death (including other, specify text [if applicable]). An additional listing of deaths will include the subject number, first UT-15C dose in TDE-PH-311 study, last UT-15C dose (day) in TDE-PH-311 study, date of death (day), and cause of death. The summary of deaths will be presented by the parent study and overall and will include the number (percent) of subjects who died (including those within 30 days of study participation) and their causes of death.

Time to death will be calculated as:

(the death date – the date of the first UT-15C dosing in TDE-PH-311 study)

The Kaplan-Meier (K-M) estimator will be provided for the time to death, and K-M plots will be provided by treatment group in the parent study.

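### Serious AEs, AE withdrawals, disease-related events and drop-out are summarised without exposure or censoring adjustment, so their percentages cannot be compared across data cuts and may not be comparable across parent arms

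*SAP*

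**What the plan says.** **Adverse events (SAP 11.1).** The summaries of serious, severe and related AEs and of AEs "leading to permanent discontinuation of UT-15C will include the number of subjects (percent of subjects) and number of events for each reported PT". These are Tables 14.3.1.3 to 14.3.1.7. One further table, 14.3.1.9, gives events per patient-year by preferred term for all AEs, without splitting them by seriousness or withdrawal. AEs still ongoing from TDE-PH-310 are included in the summaries.

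**Disease-related events (SAP 11.2, Table 14.3.1.8).** "The summary will include the number (percent) of subjects who reported each symptom by treatment group in the parent study and overall". The listing is yes/no per subject, with no dates and no event count.

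**Disposition (SAP 9.1, Table 14.1.1).** The summary includes "the number (percent) of subjects by treatment group who completed the study without early termination", the number completing treatment by each visit reached, and discontinuations with reasons. Total subject-years are summarised by parent arm and overall.

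**Deaths (SAP 11.3).** Table 14.3.2.2 "will include the number (percent) of subjects who died", and a Kaplan-Meier estimator of time to death is also planned, with plots by parent arm (Figure 14.2.1).

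**Entry and data cuts.** The eligibility summary in the protocol synopsis admits subjects who "Discontinued due to clinical worsening in TDE-PH-310", and also everyone still in the parent study when it closes. At that closure "a data cut for the TDE-PH-311 study will be performed" (SAP 5), with further cuts and a final analysis later. Follow-up ends when the drug becomes available in each territory or the sponsor stops the study (SAP 3). Protocol 3.6 expects about 6 years.

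**The concern.** A percentage of subjects with an event has a clear meaning only if the time over which they were watched is stated and similar. Here it ranges from almost nothing to years. Subjects who enter at parent closure have little or no follow-up at the first cut, while those who entered after an earlier worsening event may have a good deal. A crude percentage then rises from cut to cut even if the risk per year is constant.

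It may also differ between parent arms with no difference in risk, if the arms differ in how many subjects entered early. Protocol 1.4 hypothesises that the study drug delays clinical worsening. If so, more former-placebo subjects would enter early and be watched longer.

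Long-term safety is a stated objective (protocol 2.2, SAP 2.1), and the tables without adjustment include those for the more serious outcomes. The SAP accepts exposure adjustment for AEs as a whole but does not extend it to them.

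**Working it through.** **No design figure to reproduce.** "No formal sample size calculation has been conducted" (SAP 6), and no event rate or follow-up time by arm is given for TDE-PH-311. The nearest figures are for the earlier extension, TDE-PH-304 (protocol 1.2.4). There, 896 subjects × 138.8 weeks × 7/365.25 = 2383 patient-years, against 2377.7 stated, so the figures agree closely. Mean exposure was 2.66 years and the maximum 8.53. The number of subjects contributing to the mean dose fell from 605 at 1 year (605/896 = 68%) to 37 at 7 years (4%). Wide spread in follow-up is therefore realistic in such a study.

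**Effect of the data cut.** Assume a constant hazard h = 0.30 per year and the same follow-up t for everyone. The crude percentage is 1 − exp(−ht):

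| Follow-up | Crude % |
|---|---|
| 6 months | 13.9 |
| 1 year | 25.9 |
| 2 years | 45.1 |
| 4 years | 69.9 |

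The reverse also occurs: 0.30 per year over 1 year and 0.15 per year over 2 years both give 25.9%, so a twofold difference in risk can be hidden.

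**Effect between parent arms at the first cut.** All inputs are assumptions:
- the same hazard, 0.30 per year, in both arms;
- early-entry share of 40% (former placebo) and 28% (former UT-15C);
- follow-up of early entrants uniform on 0 to 3 years;
- 0.1 year for everyone else.

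Among early entrants, 1 − (1 − exp(−0.9))/0.9 = 0.341 have an event. Among closure entrants, 1 − exp(−0.03) = 0.030.
- Former placebo: 0.40 × 0.341 + 0.60 × 0.030 = 15.4%
- Former UT-15C: 0.28 × 0.341 + 0.72 × 0.030 = 11.7%
- Ratio 1.32, with identical risk

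**Sensitivity.** Crossing shares of 36–40% with 26–28% and hazards of 0.1 to 0.6 gives ratios from about 1.20 (36% vs 28%, h = 0.6) to 1.41 (40% vs 26%, h = 0.1). With equal shares the ratio is 1.

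**Later cuts.** Give every subject the same extra follow-up s, with no drop-out. The event proportions become 1 − exp(−0.3s) × (1 − 0.341) for early entrants and 1 − exp(−0.3(s + 0.1)) for the rest.
- s = 1 year: 37.3% vs 34.6%, ratio 1.08
- s = 2 years: 53.6% vs 51.5%, ratio 1.04

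The between-arm effect is thus mainly a first-cut problem. The rise from cut to cut persists.

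**What adjustment does in the same model.** Under a constant hazard, mean time at risk is the event proportion divided by h: 0.154/0.30 = 0.513 year per former-placebo subject and 0.117/0.30 = 0.389 year per former-UT-15C subject. First events per 100 patient-years at risk are then 30 in both arms.

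With total exposure as the denominator, as disease-related events require, mean exposure is 0.40 × 1.5 + 0.60 × 0.1 = 0.66 year and 0.28 × 1.5 + 0.72 × 0.1 = 0.492 year. The rates are 0.154/0.66 = 23.3 and 0.117/0.492 = 23.7 per 100 patient-years. The arms come close together, but the level is below the true 30, so this rate should be labelled approximate.

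**The case against.** **Much is already planned.** The serious-AE and withdrawal tables carry event counts, and subject-years are summarised by arm, so a reader can divide one by the other. This stands for a crude event rate. It does not give a follow-up-adjusted figure for subjects affected, and disease-related events have no event count to divide. Nor does Table 14.3.1.9 fill that gap. Under protocol 9.1.3, listed events attributed to progression are not recorded as AEs unless they are serious, possibly caused by the drug or more severe than expected.

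**Drop-out is shown by visit.** True, but the number completing treatment by each visit reached does not separate subjects who stopped from those not yet followed that far at the cut.

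**The study is descriptive.** "No formal hypothesis testing is planned" (protocol 10.3). That limits the consequences, and it would be too strong to say that the safety figures mislead. A percentage without a time base is still hard to interpret across cuts.

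**Two stronger readings are tempting.** One is that deaths, too, are reported only crudely. They are not: SAP 11.3 and Figure 14.2.1 plan Kaplan-Meier by parent arm. The other is that the tables will predictably make former-placebo subjects look worse. That depends on a parent-study result that is not in these documents, and on entry patterns that they do not give.

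**Adjustment is not a cure.** Early entrants have already had a worsening event and may carry higher risk. Former-placebo subjects start titration anew (protocol 6.1), so a constant hazard is doubtful. Both points stand: patient-year rates correct for length of follow-up only.

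**Conclusion.** The point holds for serious, severe and related AEs, AEs leading to discontinuation, disease-related events and drop-out. None has an exposure-adjusted or censoring-adjusted summary, and with open-ended follow-up and several cuts their percentages cannot be compared from one cut to the next.

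Comparison between parent arms is less certain. An imbalance is plausible at the first cut, but neither its existence nor its direction is documented. The ratio of 1.32 (about 1.20 to 1.41) illustrates what could happen under assumed hazards, entry shares and follow-up. It is not an estimate for this trial, and in the same model it shrinks to 1.08 and then 1.04 with one and two further years.

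The point does not extend to deaths or to AEs taken all together. It is a worthwhile reporting improvement, not a flaw in the study design.

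**What to change.** - **Tables 14.3.1.3 to 14.3.1.7:** add subjects with a first event per 100 patient-years at risk, by parent arm and overall. Time at risk runs from the first TDE-PH-311 dose to the first event, otherwise to the end of exposure or the data cut. Count only events with onset on or after that first dose, and show AEs ongoing from the parent study separately, because time to first event is undefined for them.
- **Table 14.3.1.8:** add subjects with the event per 100 patient-years of total exposure, labelled approximate because the listing has no event dates.
- **Table 14.1.1:** add a censoring-adjusted estimate of UT-15C discontinuation at fixed weeks (for example 24, 48 and 96), by parent arm and overall. Censor subjects still on treatment at the cut, and state whether death counts as a discontinuation or as a competing event.
- Keep the crude percentages beside these. No change is needed for deaths.

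The cost is SAP wording and extra table columns. AE onset dates, first and last dose dates and cut-off dates are already planned for the listings (SAP 9.1 and 11.1), so no new data are needed. The downside is longer tables. The text should also say that these rates do not remove differences in underlying risk or allow for a hazard that changes over time.
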